## Abstract

**Background:** Antidepressants are commonly prescribed by primary care providers for treating depression, anxiety, and other conditions. A trial and error approach is typically used to identify effective therapy. Treatment efficacy and safety of many antidepressants can vary based on the presence of certain diseases and metabolism gene types. Pharmacogenomic (PGx) testing provides phenotypic classification of individuals as poor, intermediate, extensive, and ultra-rapid CYP450 metabolizers. This allows more accurate drug selection for efficacy and dosing to minimize toxicity.

**Objective:** To determine the preliminary effectiveness of PGx testing for selection of effective antidepressant, medication adherence, depressive symptoms, and healthcare utilization. To determine acceptability of PGx testing in primary care among patients and providers.

**Methods:** This is a 6-month randomized, wait-listed, controlled pilot trial conducted in 6 department of family medicine (DFM) clinics at the University of Michigan (UM). We will enroll physicians practicing at a UM DFM clinical site who are willing to utilize PGx test results in conjunction with treating patients prescribed certain antidepressants. We will also enroll patients of these DFM physicians who are adults with a new prescription for an antidepressant (within the past 4 weeks) including patients who have switched to a new antidepressant from another antidepressant or have added on a new antidepressant to current antidepressant therapy. Patients are excluded if taking an antidepressant for more than 4 weeks and if they have had PGx testing in the past.

Physician participants will complete a baseline survey to assess demographics, and knowledge, acceptability and utility of PGx testing for this population. At the conclusion of the study, physician participants will complete a semi-structured interview to assess knowledge, satisfaction, feasibility, acceptability, effectiveness, barriers to widespread adoption, and utility of PGx testing.

All patients will complete a baseline, 3-, and 6-month assessment; control patients will have an additional 9-month assessment. Data to be collected include reasons for antidepressant use, depression and anxiety symptoms and severity, functional health status (SF-12), PGx knowledge, work status changes, demographic information, physician and emergency department visits, adverse effects, and medication alterations and adherence.

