### **5.4.2 Patient Participants**

To be included in this pilot trial, participants must:

- Be a patient of a participating physician
- Have a new prescription for a certain antidepressant recorded in MiChart (within the previous 4 weeks prior to screening)
- Be currently taking the new antidepressant
- Be willing to undergo PGx testing via single tube blood draw
- Be at least 18 years old

Participants will be excluded from this pilot trial if they:

- Do not speak English
- Have previously undergone PGx testing
- Are unable to provide their own consent to participate in the study
- Have been taking the new targeted antidepressant for longer than 4 weeks (prior to screening)

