### **5.5.2 Patient Participants**

Patient participants will be screened for inclusion/exclusion criteria prior to consent and enrollment. After enrollment, all patient participants will complete a baseline, 3-, and 6-month assessment. Control patients will have an additional 9-month assessment of the previously mentioned items. All baseline data will be collected via paper forms and then transferred into REDCap, whereas 3-, 6-, and 9-month assessments will be conducted via phone and entered directly into REDCap by study personnel. The constructs, measures, and data collection times are shown in Table 2. In addition to these measures collected during data collection visits, data will be extracted from MiChart to document treatment, including medication changes, and healthcare utilization for patient participants during the study. We will also extract any available PHQ-9 and GAD-7 data, which is now collected as a part of routine clinical practice. Surveys/interviews will be audio recorded when permitted by participants.

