**Table 2. Patient Participant Measures**

Construct	Measure	Assessment Time			
		Baseline (via paper survey)	3 months (via phone)	6 months (via phone)	9 months (Control Only; via phone)
Reason antidepressant was prescribed		X	X	X	X
Depression Symptoms and Severity	Personal Health Questionnaire Depression Scale (PHQ-8)	X	X	X	X
Anxiety Symptoms and Severity	Generalized Anxiety Disorder 7-Item Scale (GAD-7)	X	X	X	X
Functional Health Status	12-Item Short Form Survey (SF-12)	X	X	X	X
PGx Knowledge	Investigator Developed	X			X
Missed days of work	Work Productivity and Activity Impairment Questionnaire (WPAI)	X	X	X	X
Demographic information		X			
Health history	Smoking history, BMI	X			
Healthcare utilization	Physician visits, hospital and ER admissions	X	X	X	X
Adverse Drug Reactions	Antidepressant Side- Effect Checklist (ASEC)	X	X	X	X
Medication and medication changes	Medications prescribed and number of medication changes	X	X	X	X
Medication Adherence	Adherence to Refills and Medication Scale (ARMS)	X	X	X	X
	Pill count	X	X	X	X
	Three-Item Self-rated Adherence Scale	X	X	X	X

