## 5.6 Data Analyses

In this study, we expect to enroll up to 30 physician participants and expect a retention rate of 90-100%. We also expect to enroll about 100 patient participants and expect a retention rate of 80% at the completion of this study.

Data from this study will be analyzed by the study statistician. Survey data will be analyzed using descriptive statistics. Multiple-choice questions will be analyzed using standard quantitative techniques including Chi square and t-test. Open-ended responses will be independently coded using qualitative methods, including any transcripts that result from the recorded survey responses.

Independent sample t-tests will be used to compare outcomes between intervention and control groups at each time point, as well as at similar time points after test results were released to physicians (i.e. baseline for intervention vs. 3 month for control group). Linear mixed models will assess the change in outcomes, as well as whether the change is similar between groups. This will be done by including time, study group, and a time by study group interaction as predictors of each outcome. Time will be considered in two ways, first as the time in study, and secondly as time since test results were released to physicians. In the latter, only data from 3-month to 9-month will be included for the control group, and baseline to 6-month for intervention group, due to timing of test result release. Models will be adjusted for patient demographics.

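### Baseline counts of medication changes and physician visits may include the prescribing event that qualified the patient, so modelled change from baseline in these counts cannot be read as a PGx effect

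*Combined protocol and SAP*

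**What the plan says.** Entry (section 5.4.2) requires that a patient "Have a new prescription for a certain antidepressant recorded in MiChart (within the previous 4 weeks prior to screening"). Patients are excluded if they "Have been taking the new targeted antidepressant for longer than 4 weeks (prior to screening"). The Abstract makes clear that this covers more than first starts, "including patients who have switched to a new antidepressant from another antidepressant or have added on a new antidepressant to current antidepressant therapy".

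Table 2 lists "Medications prescribed and number of medication changes" and "Physician visits, hospital and ER admissions" at baseline, 3 and 6 months, and at 9 months for controls. It gives neither a look-back window nor a rule for leaving out the qualifying prescription or its visit. Section 5.5.2 adds that "data will be extracted from MiChart to document treatment, including medication changes, and healthcare utilization for patient participants during the study", which names no period before enrolment.

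On analysis, section 5.6 states: "Linear mixed models will assess the change in outcomes, as well as whether the change is similar between groups". It goes on: "This will be done by including time, study group, and a time by study group interaction as predictors of each outcome". The models are run on time in study and again on time since results were released. On the second scale the intervention arm contributes baseline to month 6 and the control arm month 3 to month 9. Section 5.6 also plans t-tests between the arms at each visit and at matching points relative to release; its example is the intervention arm at baseline against the control arm at month 3.

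**The concern.** A patient is in the trial because something was just prescribed. A baseline count that looks back over that moment includes at least one event by rule of entry for switches and add-ons, and for first starts if a start is counted as a change. It will often include a physician visit as well. Follow-up windows contain no such forced event. Because section 5.6 treats the baseline value as one of the responses, the time effect mixes this selection artefact with any real change.

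As an illustration with interval counts, take a patient who is switched once, enters, and never changes drug again. That patient scores 1, 0, 0 and appears to improve by one change, although nothing happened after enrolment.

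The Abstract lists healthcare utilization under preliminary effectiveness, so a fall in visits could be taken as benefit. On the time-since-release scale the artefact also enters a comparison between arms, where it could be mistaken for a treatment difference.

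**Working it through.** The plan states no power, significance level, effect size or event rate, so there is no figure of its own to reproduce. The only usable inputs are about 100 patients, equal allocation after baseline, and 80% retention: 100 × 0.80 = 80, or 40 per arm.

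**Assumptions not in the documents, shown as ranges**
- r: background events per 3 months, 0.2 to 3, constant over time
- W: baseline look-back in months; 4 weeks = 0.92, or 3
- q: share of patients whose entry event is counted at baseline; 1, 0.7 or 0
- Follow-up windows of 3 months, and no PGx effect

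**Step 1: change from baseline within an arm.** The expected baseline count is q + r·W/3 and each follow-up count is r, so the expected change is r − (q + r·W/3).

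- W = 3, q = 1: r − (1 + r) = −1.0 at any r
- W = 3, q = 0.7: −0.7 at any r
- W = 3, q = 0 (entry event excluded): 0
- W = 0.92, q = 1:

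| r per 3 months | 0.2 | 0.5 | 1 | 1.5 | 2 | 3 |
|---|---|---|---|---|---|---|
| Expected change | −0.86 | −0.65 | −0.31 | +0.04 | +0.39 | +1.08 |

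With the 4-week window the sign turns where r = q/(1 − W/3): 1/(1 − 0.307) = 1.44 events per 3 months, or 1.01 if q = 0.7.

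**Step 2: time by group on time in study.** Both arms have the same expected change, so the difference is 0.

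**Step 3: time by group on time since release.** The intervention arm runs from baseline, giving r − (q + r·W/3). The control arm runs from month 3 to month 9, giving r − r = 0. The spurious difference is therefore the whole of the step 1 quantity: −1.0 with W = 3 and q = 1.

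**Step 4: aligned t-test.** Intervention baseline minus control month 3 is (q + r·W/3) − r, which is +1.0 with W = 3 and q = 1.

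**Step 5: how often this looks significant with no PGx effect.** Simulation used overdispersed counts (gamma-Poisson, shape 2), 40 per arm, 4000 runs and a two-sided 5% level. T-tests on each patient's 6-month change stood in for the mixed-model terms. With W = 3 and q = 1:

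| Test | r = 0.5 | r = 1 | r = 2 |
|---|---|---|---|
| Time effect, arms pooled | 100% | 100% | 99% |
| Time by group, time in study | 5% | 5% | 5% |
| Time by group, time since release | 99% | 88% | 60% |
| Aligned t-test | 100% | 95% | 61% |

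With W = 3 and q = 0.7, the release-scale interaction is significant in 84%, 58% and 34% of runs at the same rates. With W = 0.92 and q = 1 it is 87%, 19% and 14%, the last in the opposite direction. Time by group on time in study stays at 4–6% in every scenario tried.

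**The case against.** The strongest reply is that the problem depends on definitions the plan does not give.

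- The look-back is unstated. The 4 weeks run back from screening, and screening comes before consent and baseline, so a short look-back from baseline could miss the qualifying prescription.
- Table 2 puts drugs prescribed and number of changes in one row, so the baseline mark may mean only a drug list. A first start need not count as a change. If baseline is set to zero, or counts run cumulatively from the qualifying prescription, the artefact in medication changes disappears.
- Entry requires a recorded prescription, not a visit.
- Chart extraction covers the study period, so the point rests on the baseline survey item.
- Randomisation follows baseline, so a shared trend is what the control arm is there to separate from an effect.
- These are lesser outcomes. Aim 1 concerns contraindicated prescriptions, Aim 2 names symptoms and adherence, and utilization is an objective only in the Abstract.

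All of this stands as a limit on the claim, which has to be conditional. Two stronger readings are tempting and unsupported. A reader might infer that the counts must fall in everyone. The fall is in the mean: even with a 3-month window and every entry event counted, individual counts fell in only 61–82% of simulated patients, and with a 4-week window the mean can rise. A reader might also infer that the randomised comparison as a whole is biased; steps 2 and 5 show that it is not on time in study.

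The reply does not rescue the within-arm change, since a result whose sign depends on an unstated window cannot be interpreted. Nor does the control arm help on the release scale, where the two arms start from different kinds of observation.

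**Conclusion.** The concern holds in conditional form. If the baseline count reaches the qualifying event, change from baseline in medication changes and physician visits contains a selection artefact. Its size is about one event per patient on average with equal 3-month windows and every entry event counted, and it scales with the share counted. With unequal windows its size and sign depend on the background rate. These figures rest on assumed rates and windows, a constant background rate and 3-month follow-up counts.

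The affected analyses are the time effect on both scales, the time-by-group term on time since release, and the aligned t-test that uses the intervention baseline. Not affected are same-visit comparisons at 3 and 6 months, time by group on time in study, and the primary outcome, which is not a count of changes or visits. The consequence is confined to two secondary counts, but it goes beyond missing detail, because the stated analysis can be replaced by a better one at little cost.

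**What to change.** In section 5.6, for medication changes and physician visits only:

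1. Do not use the baseline count as a response on either time scale.
2. Compare the arms on events counted in post-randomisation intervals of equal length, 0–3 and 3–6 months, noting that controls' results are released at month 3. The first interval then compares released with withheld results, and the second compares earlier with later release.
3. If a baseline count is used as a covariate, state its look-back window and, where dates allow, exclude the qualifying prescription and its visit.
4. Report change from baseline in these counts, if at all, as descriptive and not as evidence of effectiveness.

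This takes a few sentences. The arm comparison needs no data beyond what is already planned. Removing the qualifying visit from a covariate needs dated events, which a paper baseline form and study-period chart extraction may not supply; in that case the covariate can be left out. The price is the loss of a before-after statement for two secondary counts.

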Patient participants will meet with study staff for consent and baseline data collection at a Michigan Clinical Research Unit (MCRU) in either Domino's Farms or the Cardiovascular Center. Once consent and baseline data collection are complete, participants will have their blood drawn by MCRU laboratory staff. A single 4 mL Lavender top EDTA tube of blood will be drawn. Once the blood draw is complete, study staff will send the sample to Progenity for analysis. After the baseline assessment is complete, patient participants will be randomized equally to either have their test results sent immediately to their participating primary care physicians once available, or to have their test results sent in three months. Randomization will be stratified by physician in ten block units to ensure balance by physician. PharmDs on the research team ([name] and [name]) will be available to consult with physician participants at any time during the study; however, our study PharmDs will meet with each participating physician at least once, when their first patient PGx test results are available to provide general, as well as patient specific education about the PGx test and results. These consultations will help physicians to interpret PGx test results, and may help to guide treatment decisions, if necessary. Study pharmacists or staff will not

provide PGx results to patients; it is up to the patient's physician to provide this information if he/she feels it is appropriate. Likewise, although study pharmacists may make treatment recommendations based on the PGx test results, it is up to the treating physician to decide whether to act on those recommendations. All intervention patient participants will be followed for a total of 6 months, with phone-based follow-up assessments occurring at 3- and 6-months. All control patients will be followed for 9 months, with phone-based follow-up assessments occurring at 3-, 6-, and 9-months. Please see Figure 2 for patient participant study flow.

Figure 1. Physician Participant Study Flow

[figure not shown]
[figure not shown]

Figure 2: Patient Participant Study Flow

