Physicians and patients enrolled in this study will be exposed to minimal risk. Participants in both arms of the study will undergo PGx testing. Physicians for intervention group participants will receive PGx test results as soon as they are available, whereas those participants in the waitlisted control group will receive their test results three months after enrollment. Because the current standard of care does not involve the use of PGx testing, our waitlisted control group is not exposed to any additional risk above and beyond usual care. To clarify, the intervention under investigation in this study is the PGx test. We will not directly intervene in the clinical care of a patient, as all clinical decision making is at the discretion of the physician managing a patient's care. All participants in this study may benefit because their antidepressant medication may be tailored to their pharmacogenomic profile. Although both populations of participants run risks associated with breaches of privacy due to electronic storage of study data, every effort will be made to minimize these risks.

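### The time-by-group interaction has no stated time coding or target contrast; if time is linear over unequal follow-up, ordinary recovery can pass for a PGx effect on continuous outcomes

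*Combined protocol and SAP*

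**What the plan says.** Section 5.6 plans linear mixed models to judge whether change differs between the arms: "This will be done by including time, study group, and a time by study group interaction as predictors of each outcome". The models are run on two time scales: "Time will be considered in two ways, first as the time in study, and secondly as time since test results were released to physicians". A restriction on visits is given for the second scale only: "In the latter, only data from 3-month to 9-month will be included for the control group, and baseline to 6-month for intervention group".

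Section 5.1 sets unequal follow-up: "All intervention patient participants will be followed for a total of 6 months", but "All control patients will be followed for 9 months". Section 5.5.2 agrees: "Control patients will have an additional 9-month assessment of the previously mentioned items". Section 5.1 also has the control arm randomised "or to have their test results sent in three months".

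Section 5.6 separately plans two-sample t-tests between the arms at every assessment, which includes 3 months. Aims 1 and 2 in section 3.0 both run from baseline to six months. The plan does not state how time is coded, which model contrast is the PGx effect, whether the control 9-month visit enters the time-in-study model, or a significance level.

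**The concern.** Because visits are limited only on the second time scale, the natural reading is that the time-in-study model uses everything collected: months 0, 3 and 6 for intervention and 0, 3, 6 and 9 for control. What the interaction then measures depends on the coding of time.

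- **Linear time.** The interaction is a difference between two straight-line slopes fitted over different windows. If patients improve early and then level off, the arm followed longer has the flatter slope, even if testing does nothing.
- **Linear time, both arms cut to 0-6 months.** The window problem goes away. But controls get their results at 3 months, so a lasting effect can reach both arms by month 6 and cancel out of the slope difference.
- **Visit as a factor.** The false signal disappears. But the 6-month contrast compares two arms that both have results, and the 9-month cell has no comparator.

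Only the period from baseline to 3 months compares randomised arms with and without results. The plan does not single it out. At stake is whether the model result reported under Aim 2 can be read as an effect of testing.

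**Working it through.** The plan gives no power, significance level or effect size, so there is no figure to reproduce.

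**Inputs from the documents.** About 100 patients, equal allocation and 80% retention (sections 5.1 and 5.6): 100 x 0.80 / 2 = 40 per arm. Visits and release time are as quoted above.

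**Assumed inputs.** Outcome SD 5 points; within-patient correlation r of 0.3, 0.5 or 0.7 (random intercept); two-sided 5% test; mean change from baseline of 0/-3/-4/-4 points at 0/3/6/9 months. The shape is plausible from the documents: section 2.0 puts clinical effect at two to four weeks, and section 5.4.2 admits patients no more than 4 weeks into the new drug at screening.

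**1. Linear time, no PGx effect, intervention 0-6 v control 0-9.** Time is in units of 3 months. The sum of squared time deviations is 2 for visits 0, 1, 2 and 5 for visits 0, 1, 2, 3.

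- Intervention slope = (-4 - 0) / 2 = -2.0
- Control slope = [-1.5(0) - 0.5(-3) + 0.5(-4) + 1.5(-4)] / 5 = -6.5 / 5 = -1.3
- Spurious difference = -2.0 - (-1.3) = -0.7 points per 3 months, favouring intervention
- SE = sqrt[25(1 - r)/40 x (1/2 + 1/5)]

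| r | SE | difference/SE | rejection |
|---|---|---|---|
| 0.3 | 0.553 | -1.26 | 24% |
| 0.5 | 0.468 | -1.50 | 32% |
| 0.7 | 0.362 | -1.93 | 49% |

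Other no-effect curves: scores of 12/8.5/7.5/7 give -0.65 per 3 months and 22-43% rejection; 12/8/7/7 gives -0.9 and 37-70%. If recovery is exactly linear, the difference is 0 and rejection is 5%.

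**2. Linear time, lasting effect d.** The intervention arm gains d from month 3 and the control arm gains it from month 6.

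- Both arms 0-6: intervention (0, d, d) adds d/2 and control (0, 0, d) adds d/2. The difference is 0 and rejection is 5%.
- Control 0-9: control (0, 0, d, d) adds (0.5d + 1.5d)/5 = 0.4d. The difference is 0.1d, or -0.3 per 3 months for a 3-point improvement. With no background recovery, rejection is 8-13% over the three correlations.
- Control 0-9 with the recovery curve of step 1: -0.7 - 0.3 = -1.0 per 3 months, rejected in about 57% of trials at r = 0.5. Seven tenths of that difference is bias.

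**3. Time since release, no PGx effect, same curve.** The windows are equal, but the control arm enters later in recovery.

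- Intervention slope over 0, -3, -4 = -2.0
- Control slope over -3, -4, -4 = -0.5
- Spurious difference = -1.5 points per 3 months
- SE = sqrt[25(1 - r)/40 x (1/2 + 1/2)] = 0.661, 0.559, 0.433
- Rejection: 62%, 77%, 93%

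**4. The 3-month contrast, 3-point effect.**

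- Planned t-test: SE = 5 x sqrt(2/40) = 1.118; 3/1.118 = 2.68; power about 77%. With 50 per arm it is 85%.
- With baseline as covariate: SE = 1.118 x sqrt(1 - r^2). Power is 80%, 87% and 96% at r = 0.3, 0.5 and 0.7.

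**The case against.** **Linear time is not in the text.** A linear mixed model is a class of model, and the wording fits visit as a factor equally well. With a factor, the no-effect contrast has expectation 0. This stands: the false-positive rates above are conditional on linear coding. What remains under a factor is that no contrast is named and that only the 3-month one compares tested with untested care.

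**Use of control months 0-9 is inferred.** The plan calls this a six-month study, and the aims stop at six months. The inference from the one-sided visit restriction is fair, but it is not a statement.

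**A valid comparison is already planned.** The 3-month t-test has about 77% power for 3 points. A reader might infer that the plan as a whole would miss an early effect. The documents do not support that; the insensitivity belongs to the slope test. The t-test is, however, unadjusted for baseline, one of several, and not designated as the PGx contrast.

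**The two failures do not occur together.** A reader might infer that one model both finds false effects and has almost no power. The inflated rejection needs the control 9-month visit; the exact cancellation needs it left out.

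**Aim 1 is a proportion.** A reader might also infer that the interaction cannot serve either aim. The arithmetic uses a continuous score with a symptom-recovery curve and says nothing about prescribing of contraindicated drugs.

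**This is a pilot without a decision rule.** True, so rejection rates here describe how misleading the result could be, not a breached error rate. Aim 2 nevertheless sets out to determine an effect.

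**Conclusion.** The certain defect is one of specification: section 5.6 rests the comparison of change on a single interaction without stating the coding of time, the target contrast or the use of the control 9-month visit.

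The consequence depends on the coding. With linear time over all visits and front-loaded recovery, a spurious benefit of about 0.7 points per 3 months arises, with 24-49% rejection under the main assumed curve. With both arms limited to 0-6 months, that bias goes, but a lasting effect that controls gain after release gives a slope difference of 0. The time-since-release model does not rescue the plan, since its equal windows cover different stages of recovery (62-93% rejection with no effect).

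SD, correlation and recovery curve are assumptions, and the bias vanishes if recovery is linear. The conclusion is limited to continuous outcomes such as symptom scores. It takes the 3-month assessment as made before release could influence control patients.

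**What to change.** In section 5.6, for the continuous outcomes:

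- Enter visit as a categorical factor and adjust for the baseline value of the outcome.
- Name the 3-month difference between arms as the randomised PGx contrast.
- Leave the control 9-month visit out of the time-in-study comparison between arms.
- Keep the 6-month comparison that the aims name, but label it as early versus delayed release of results.
- Report the 9-month and time-since-release results as descriptive.

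No new data are needed, and the change helps under either coding of time. The cost is interpretive: the 6-month result between arms becomes supportive evidence and no longer a test of tested versus untested care. Since Aim 2 is framed at six months, its text should be aligned with this distinction.

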## 3.0 Objectives

PGx testing could greatly improve the use of antidepressants by aiding prescribers in identifying proper medications for individual patients; thus potentially improving medication adherence, as well as reducing symptoms and antidepressant side effects.

This pilot study will explore the use of PGx testing in primary care, and is guided by several specific aims:

Specific Aim 1: To determine the effect of PGx testing on the primary outcome of physician treatment decisions, as measured by the change in the proportion of patients who are prescribed medications at baseline that are contraindicated according to the PGx test, compared to the proportion at six-month follow-up.

Specific Aim 2: To determine the effect of PGx testing on secondary outcomes measures of interest, including change in symptoms and severity and medication adherence from baseline to six-month follow-up.

Specific Aim 3: To determine the acceptability of PGx testing in primary care among patients and physicians.

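### Re-zeroing time at result release sets intervention months 0–6 against control months 3–9, so time on the new drug is confounded with release of the PGx results

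*Combined protocol and SAP*

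**What the plan says.** Section 5.1 randomises patients equally to have results sent to their physician once available, "or to have their test results sent in three months". Section 5.6 compares the arms at each study time point and then again at matching times after release, giving as its example "i.e. baseline for intervention vs. 3 month for control group". For the mixed models with a time-by-group interaction, "Time will be considered in two ways, first as the time in study, and secondly as time since test results were released to physicians". On the second scale, "only data from 3-month to 9-month will be included for the control group, and baseline to 6-month for intervention group". The only adjustment named is this: "Models will be adjusted for patient demographics".

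The aims in section 3.0 use study time. Aim 1 concerns the proportion of patients on drugs "contraindicated according to the PGx test, compared to the proportion at six-month follow-up". Aim 2 is worded "To determine the effect of PGx testing on secondary outcomes measures of interest". The outcomes it lists run over the same six months: "including change in symptoms and severity and medication adherence from baseline to six-month follow-up". Section 5.6 lists time in study first, but it neither ranks the two scales nor says how aligned results may be read.

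**The concern.** Section 5.4.2 admits patients whose new prescription dates from the 4 weeks before screening and who are taking the drug. Section 2.0 puts onset of clinical effect at two to four weeks. Months 0–3 are therefore when symptoms are likely to change fastest, and they fall only in the intervention window. Months 6–9 fall only in the control window, and months 3–6 fall in both. At aligned time zero, controls have been on drug about three months longer than intervention patients.

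On this scale both arms have their results released, so the contrast is not tested against untested. What differs systematically is the stretch of the treatment course being observed. If the aligned interaction were reported under the aim of determining the effect of PGx testing, ordinary early drug response could pass for a benefit of the test. The plan's own t-test example lies at or before release in both arms, so a difference there cannot be a PGx effect. It also compares a paper survey with a phone interview (section 5.5.2).

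**Working it through.** The documents give no alpha, SD, correlation or symptom course, so there is no stated figure to reproduce.

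**From the documents:** about 100 patients, equal allocation, 80% retention: 100 × 0.5 × 0.8 = 40 per arm.

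**Assumed:** two-sided alpha 0.05; SD 5 points; within-patient correlation 0.5; mean falls of *f*, 1 and 0.5 points over months 0–3, 3–6 and 6–9, the same in both arms; no PGx effect.

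**1. Aligned change contrast.** Intervention (months 0–6) falls by *f* + 1. Control (months 3–9) falls by 1 + 0.5. The difference is *f* − 0.5. SD of change = 5 × √(2 × (1 − 0.5)) = 5. SE = 5 × √(2/40) = 1.118. Noncentral t on 78 df:

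| First 3-month fall | Spurious difference | Noncentrality | Rejection |
|---|---|---|---|
| 1 | 0.5 | 0.447 | 7% |
| 2 | 1.5 | 1.342 | 26% |
| 3 | 2.5 | 2.236 | 60% |
| 4 | 3.5 | 3.130 | 87% |

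Sensitivity at *f* = 3: correlation 0.3 to 0.7 gives 46% to 81%; SD 6 to 4 gives 45% to 79%; a 6–9 month fall of 1 or 0 gives 42% or 75.5%.

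**2. Planned slope model.** Means of 12, 9, 8 and 7.5 give aligned slopes of (8 − 12)/6 = −0.667 and (7.5 − 9)/6 = −0.25 per month, a difference of −0.417. In 20,000 simulated null trials with a random intercept, the mean difference was −0.415 and rejection 60.1%, all in the direction of benefit. On time in study, rejection was 5.1%.

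**3. Aligned t-tests, *f* = 3.** The differences are 3 (month 0 vs 3), 1 (3 vs 6) and 0.5 (6 vs 9). Rejection is 75.5%, 14% and 7%, each against the intervention arm.

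**4. Part of the 3-point fall occurs before baseline.** With a quarter, a third or a half gone, the change contrast rejects 34%, 26% or 14%, and the time-zero t-test 51%, 42% or 26%.

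**5. Linear improvement, 1.5 points per 3 months.** The aligned slope test holds at 5.4%. Each aligned t-test is off by 1.5 points and rejects about 26%.

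**6. Contraindicated prescriptions.** Assumed 20% share at baseline and switching of 30%, 10% and 5% in successive three-month periods. If no one is moved onto a contraindicated drug, the share runs 20.0, 14.0, 12.6, 11.97%. The aligned difference is (12.6 − 20.0) − (11.97 − 14.0) = −5.4 points. Other cases use the same recursion; rejection rates are from 20,000 simulated null trials:

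| Case | Shift, points | Rejection |
|---|---|---|
| Equal switching, landing at the base share | 0.0 | 5% |
| Patients on other drugs switch half as often | −2.1 | 6% |
| No one switched onto a contraindicated drug | −5.4 | 18% |
| Landing at 1.5 times the base share | +2.7 | 6% |

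Negative values favour the intervention arm. A constant 15% per period gives shifts of 0 to 0.8 points and 5% rejection. Across the 10% and 30% shares tried (switching 10/5/5% and 40/10/5%), rejection ran from below 2% to 50%, the top figure again needing no one to be switched on.

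**The case against.** The best defence is that the analyses matching Aims 1 and 2 are intact: both aims run from baseline to six months, and the time-in-study tests come first. This is a pilot, and section 5.6 says only that the models ask whether change is similar between groups. The windows may truly differ, so harm arises only if the aligned result is reported as a PGx effect. That limits the severity. It does not answer the point, because the plan specifies these tests, ranks nothing and gives no caution, while the aims speak of determining the effect of PGx testing.

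Four narrower objections stand in part:

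- The aligned interaction is biased only by a non-linear course, because under a linear one the group term absorbs the shift. The aligned t-tests are biased by any trend.
- Some response may precede baseline, and the sample includes switchers and patients treated for conditions other than depression. Step 4 shows that the bias shrinks but does not vanish.
- The Aim 1 outcome is little affected in most of the mid-case scenarios, and the 18% needs an extreme switching pattern.
- The intervention arm contributes the same months on both scales, so its own trend is no worse when aligned. It still cannot be read as a PGx effect.

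A six-month main analysis has its own weakness, since controls have had results for about three months by then. The fix therefore pairs it with month 3.

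**Conclusion.** The concern holds. The release-aligned tests confound result release with time on the new drug, and the planned covariates cannot separate the two. For symptoms, a plausible early response with no PGx effect gives a change contrast that favours the intervention arm (26% to 87% rejection for first-period falls of 2 to 4 points) and a time-zero t-test that goes against it. With a linear course, only the aligned t-tests are affected. For contraindicated prescriptions the bias is conditional on switching patterns and can be nil.

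All these sizes rest on assumed SDs, correlations, symptom courses and switching rates. The mismatch of windows follows directly from section 5.6. The time-in-study comparisons keep the randomised contrast and hold about 5%. This should be fixed, but it does not undermine the trial.

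**What to change.** In section 5.6:

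- State that time in study, baseline to six months, is the main analysis, as Aims 1 and 2 imply.
- Report beside it the month-3 contrast adjusted for baseline. An unadjusted month-3 t-test is already planned. Month 3 is the one visit at which only the intervention arm's results have been released. A 3-point effect complete three months after release shows as 3 points at month 3 and 0 at month 6; built evenly over six months, it shows as 1.5 at both. In 5,000 simulated null trials the baseline-adjusted contrasts rejected 4.7% (month 3) and 4.9% (month 6).
- Use control month-3 data recorded before the results are sent.
- Drop the aligned between-arm t-tests and the aligned time-by-group test, keeping aligned summaries as descriptive with no claim of a PGx effect. Alternatively, replace them with one mixed model on all visits (0, 3, 6 for intervention; 0, 3, 6, 9 for control) with categorical time in study, study group and a time-varying term for results released.

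The cost is wording in section 5.6 plus one procedural line that the control month-3 call is completed before release, with no new data and no change of endpoint. The price is either losing the aligned between-arm tests or assuming a form for the effect after release, with the direct between-arm information on release coming mainly from month 3.
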